9.3.11. Platelets and Hemoglobin

Platelet and hemoglobin measurements are not reliable with concurrent red blood cell (RBC) and/or platelet transfusions. Therefore, platelet values obtained on the day of a blood transfusion of platelets through 7 days after the transfusion will be excluded from all analyses. Hemoglobin values obtained on the day of a blood transfusion of either whole blood or packed RBCs through 7 days after the transfusion will be excluded from all analyses. This rule will only be applied to postbaseline assessments of platelets and hemoglobin.

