4.3. Changes from Analyses Specified in the Previous Version of the SAP

Abbreviations: FACIT = Functional Assessment of Chronic Illness Therapy; PA2 = Protocol Amendment 2; SAP = statistical analysis plan; TMA = thrombotic microangiopathy

5. **DEFINITIONS**

5.1. **Primary Endpoint**

The primary efficacy endpoint of the study is complete TMA response during the 26-week randomized Treatment Period.

Complete TMA response is defined as normalization of hematologic parameters (platelet count and LDH) and \geq 30% improvement in estimated glomerular filtration rate (eGFR) from Baseline (Table 2).

Table 2:	Overview of Complete Thromb	ootic Microangiopathy Response
----------	------------------------------------	--------------------------------

		TMA Response Parameter
Complete TMA response	Hematologic response	 Normalization of platelet count (defined as platelet count ≥ 150000/µL) without transfusion support during the prior 7 days Normalization of LDH (defined as LDH
		\leq 1.5 × upper limit of normal)
	Renal response	• Improvement in eGFR of ≥ 30% compared to Baseline

Abbreviations: eGFR = estimated glomerular filtration rate; LDH = lactate dehydrogenase; TMA = thrombotic microangiopathy

If a participant is not on dialysis at Baseline, baseline eGFR will be defined as the last nonmissing assessment value prior to the start of study treatment. If a participant is on dialysis at Day 1, baseline eGFR will be set to 10 mL/min/1.73 m². If a participant is on dialysis during the entire 26-week randomized Treatment Period or through early discontinuation of study drug, then the change in eGFR will not be calculated.

For complete TMA response, participants must have met all 3 TMA response parameters simultaneously, with each component meeting the requirement at 2 separate assessments obtained at least 24 hours apart, and any measurement in between. The first laboratory value will be assessed based on central laboratory results; the second laboratory value will be assessed based on the earliest value obtained \geq 24 hours after the first value and may be based on central or local laboratory results.

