Participants will be classified as nonresponders if they do not have any TMA response observed before the following intercurrent events: treatment discontinuation or start of disallowed therapy or medicine, regardless of whether the TMA response is observed after these intercurrent events. For other participants without the above intercurrent events, whether the TMA response occurs by 26 weeks will be assessed using all available assessments within the 26-week randomized Treatment Period.

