7.1.1. Handling Missing Data

For binary endpoints, a nonresponder imputation (NRI) method will be used by categorizing any participants who have a missing value for categorical variables at a specific visit as a nonresponder for that visit. In addition, participants who have the following intercurrent events will be assigned as nonresponders, regardless of whether any response is observed after these intercurrent events: premature discontinuation of the study treatment or initiation of disallowed therapy or medicine, before observing the response for an endpoint in analysis.

For time-to-event endpoints (time to complete TMA response, time to response for each individual TMA parameter), missing data and data after intercurrent events of premature discontinuation of study treatment or initiation of disallowed therapy or medicine will be censored.

For the continuous secondary endpoint, no missing data handling will be performed. Summary statistics will be provided using observed data.

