9.3.2. Loss of TMA Response

For participants who meet the criteria for complete TMA response during the 26-week randomized Treatment Period, loss of TMA response is defined as when the participant fails to meet the criteria for 1 or more components of TMA response at a subsequent visit during the 26-week randomized Treatment Period. At least 1 parameter must fail to meet the response criteria at 2 separate assessments obtained at least 24 hours apart and any measurement in between. The first laboratory value will be assessed based on central laboratory results; the second laboratory value will be assessed based on the earliest value obtained \geq 24 hours after the first value and may be based on central or local laboratory results.

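### SAP 9.3.11 treats platelet values from a platelet transfusion through 7 days after as no data, so a low value there cannot break a response confirmation or count toward loss of response

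*SAP*

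**What the plan says.** SAP 9.3.11 calls platelet counts unreliable around transfusion and then states that "platelet values obtained on the day of a blood transfusion of platelets through 7 days after the transfusion will be excluded from all analyses". The rule works by date alone, whatever the count, and "This rule will only be applied to postbaseline assessments of platelets and hemoglobin". Nothing in 9.3.11 says that a transfused interval counts as failing the platelet criterion.

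The endpoints that use platelets are defined elsewhere:

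- **Complete TMA Response (SAP 5.1, Table 2).** Platelets must be at least 150,000/µL "without transfusion support during the prior 7 days". All three parameters must be met simultaneously, "with each component meeting the requirement at 2 separate assessments obtained at least 24 hours apart, and any measurement in between". For confirmation, "the second laboratory value will be assessed based on the earliest value obtained" at least 24 hours after the first. In participants without an intercurrent event, response "will be assessed using all available assessments within the 26-week randomized Treatment Period".
- **Loss of TMA Response (SAP 9.3.2).** "At least 1 parameter must fail to meet the response criteria at 2 separate assessments obtained at least 24 hours apart".
- **Missing binary data (SAP 7.1.1).** Nonresponder imputation (NRI) is applied by "categorizing any participants who have a missing value for categorical variables at a specific visit as a nonresponder for that visit".

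SAP 9.3.10, on the neighbouring problem of creatinine during dialysis, works differently. It drops the creatinine value but sets eGFR to 10 mL/min/1.73 m², an unfavourable value.

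**The concern.** Both response and loss are defined by runs of consecutive assessments, so it matters whether an assessment is failing or absent. A failing platelet count between two normal ones stops confirmation. An absent one does not: the next surviving value becomes the confirming value, and the in-between check has nothing to examine. Likewise, a failing count inside the window cannot be one of the two values needed for loss.

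A participant who drops to a low count, is transfused and later recovers could therefore be recorded as a confirmed responder from before the drop, or as never having lost response. The primary endpoint, time to Complete TMA Response, time to hematologic response and Loss of TMA Response are all exposed.

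**Working it through.** The plan gives no figure on this point to reproduce, so the check applies the rules to constructed cases.

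**1. The same value under the two rules.** Take a platelet count of 35,000/µL on the day of a platelet transfusion, with normal counts at the visits before and after. Under Table 2 alone it fails, because it is below 150,000/µL, and the pair around it is not confirmed. Under 9.3.11 it is excluded from all analyses, so it is not among the available assessments and cannot fail. SAP 5.1 and 9.3.11 do not say which prevails.

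**2. Reach of the window.** The window runs from transfusion day to day 7 after it, which is 8 calendar days. Protocol Table 1 schedules 12 post-baseline laboratory visits in the Treatment Period: Days 8, 15, 22, 29, 43, 57, 71, 85, 99, 127, 155 and 183. Each is removed by a transfusion on any of 8 days, so there are 12 × 8 = 96 visit removals over transfusion Days 1 to 183. A transfusion on Day 8, 15 or 22 removes two visits. The number of distinct days that remove at least one visit is 96 − 3 = 93 of 183 (one visit on 90 days, two on 3). This says how easily a single transfusion empties a visit, not how often transfusions occur.

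**3. Constructed series** (platelets in thousands/µL; LDH and eGFR held as met throughout; transfusion on Day 43):

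| Series | Platelets | Window deleted (9.3.11) | Window counted as failing |
|---|---|---|---|
| A | Day 29: 160; Day 43: 35; Day 57: 165; below 150 at all other visits | Complete TMA Response, Days 29 and 57 | No response |
| B | Response confirmed Days 15 and 22; Day 43: 40; Day 45: 60; Day 48: 80; 170 or more from Day 57 | No loss | Loss, Days 43 and 45 |
| C | Response confirmed Days 15 and 22; Day 41: 45; Day 43: 30; Day 45: 60; Day 57: 100; Day 71: 90 | Loss, Days 41 and 57 | Loss, Days 41 and 43 |

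A is a false response, B a missed loss, and C a loss whose confirmation moves by 57 − 43 = 14 days.

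**4. When responder status does not change.** If series A also had a qualifying count on Day 71, Days 57 and 71 would form a valid pair and the participant would be a responder either way. Only the response date would move, from Day 57 to Day 29, which is 28 days too early.

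**5. How much loss needs.** After Day 29 scheduled visits are 14 or 28 days apart, so an 8-day window holds at most one of them. Hiding a loss therefore needs either an extra sample inside the window, as in B, or a failing value just outside it that would have paired with the deleted one.

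**6. Size of one reclassification.** SAP 4 reports 16 enrolled and 1:1 allocation but no split by arm. Assuming 8 per arm, one participant is 1/8 = 12.5 percentage points. For example, 4/8 = 50.0% (Clopper-Pearson 95% CI 15.7 to 84.3) becomes 5/8 = 62.5% (24.5 to 91.5).

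**The case against.** - **The deletion has a proper purpose.** It stops a count raised by transfusion from qualifying as normal. That stands. The fault is only that the window becomes missing instead of not met.
- **The 7-day transfusion condition already covers it.** Table 2's requirement applies at both assessments and at any measurement between them, so a value in the window would fail. That is a fair reading of SAP 5.1, but only if the value is still in the data. 9.3.11 removes it, and a confirming value more than 7 days after transfusion passes the condition.
- **NRI repairs it.** SAP 7.1.1 makes a missing visit a nonresponse for that visit, and SAP 7.3.1 applies NRI to the primary analysis. This protects by-visit endpoints such as hematologic response at Week 26. One could read it as breaking the pair as well, but no text says that a missing visit interrupts a confirmation or counts toward loss.
- **LDH and eGFR are untouched.** This stands and narrows the point. If either of them fails as well, response is not confirmed or loss is still shown.
- **Low values outside the window remain.** This stands too. Counts before transfusion day or after day 7 are kept, as series C shows.
- **Consequences are limited.** SAP 4.2 drops hypothesis testing and treatment comparison, so only descriptive rates and curves are affected.

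**Conclusion.** The point holds as a defect in the derivation rule. As written, a low platelet count from transfusion day through day 7 cannot break a confirmation pair or contribute to loss, and neither the transfusion condition nor NRI clearly closes the gap. The possible errors are a false or too-early Complete TMA Response and a missed or delayed loss. Each requires LDH and eGFR to stay within criteria. A change in responder status also requires that no other pair of assessments qualifies. It is likely uncommon, and its frequency cannot be estimated from the documents. The 12.5 points is the effect of one participant under an assumed arm size of 8, not an expected bias.

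A reader might infer more, and the documents do not support it:

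- **Mean platelet change is biased upward.** Transfusion-raised values are deleted along with low ones, and there are no transfusion data to settle the direction.
- **Same-day samples drawn before transfusion should be kept.** Protocol 8.2.3 lists the date, units and volume of each transfusion but no time, so those samples may not be identifiable.
- **Any normal, low-with-transfusion, normal sequence creates a false responder.** Step 4 of the working shows that it often need not.

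**What to change.** In SAP 9.3.11, keep the exclusion for continuous platelet summaries. Add one sentence: for Complete TMA Response, hematologic response, time to response, the in-between check and Loss of TMA Response, any platelet assessment from the day of a platelet transfusion through 7 days after counts as not meeting the platelet criterion, rather than as missing. A cross-reference from SAP 5.1 and 9.3.2 would remove the remaining ambiguity.

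The change needs no new data, because Protocol 8.2.3 already collects transfusion dates. It brings platelets into line with the unfavourable-value approach that SAP 9.3.10 takes for eGFR on dialysis. The downside is that the response rate may be slightly lower and losses slightly more frequent.

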9.3.12. Hypertension

Hypertension will be defined as follows.

Two consecutive blood pressure measurements obtained at least 1 hour apart, where

- The systolic pressure is greater than 139 mm Hg or
- The diastolic pressure is greater than 80 mm Hg

9.3.13. EQ-5D-5L Scoring Algorithm for US TTO

EQ-5D-5L is assessed using the index scored according to the TTO value set for the US as well as the response on the VAS question.

The standard US TTO value set is used to assign a value based on the health state indicated on the questionnaire.

The following will be used to calculate STATES at each time point:

MOBILITY: 0.000 if response = 1, -0.096 if response = 2, -0.122 if response = 3, -0.237 if response = 4, -0.322 if response = 5

SELF CARE: 0.000 if response = 1, -0.089 if response = 2, -0.107 if response = 3, -0.220 if response = 4, -0.261 if response = 5

USUAL ACTIVITIES: 0.000 if response = 1, -0.068 if response = 2, -0.101 if response = 3, -0.255 if response = 4, -0.255 if response = 5

PAIN/DISCOMFORT: 0.000 if response = 1, -0.060 if response = 2, -0.098 if response = 3, -0.318 if response = 4, -0.414 if response = 5

ANXIETY/DEPRESSION: 0.000 if response = 1, -0.057 if response = 2, -0.123 if response = 3, -0.299 if response = 4, -0.321 if response = 5

US TTO score = 1 + MOBILITY + SELF CARE + USUAL ACTIVITIES + PAIN/DISCOMFORT + ANXIETY/DEPRESSION

If data for some but not all dimensions are missing at a specific time point, data for the missing dimension(s) from the last available assessment prior to the time point with missing data will be used in the US TTO calculation. If all dimensions are missing, the last available US TTO score prior to the time point with missing data will be used.

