## **8.11. Other Assessments**

### **8.11.1. Patient-Reported Outcome Measures**

Quality of life scales will be administered electronically by the Investigator or a qualified site staff member prior to other study procedures at visits specified in the Schedule of Activities (Section 1.3).

All assessments should be administered in a quiet room and should be administered electronically by the Investigator or a qualified site staff member prior to other study procedures at visits specified in the Schedules of Activities (Section 1.3). These assessments may be

recorded on paper if electronic devices are unavailable or cannot be used. If the Investigator deems that the participant is not able to self-report using any of these instruments at a particular time point, then they will not be administered to the participant.

The following quality of life scales will be administered:

- The Functional Assessment of Chronic Illness Therapy (FACT)-Fatigue scale (Section 10.11.1), Version 4.0, is a 13-item questionnaire that assesses self-reported fatigue and its impact upon daily activities and function over the preceding 7 days (Cella, 2002; Webster, 2003; Yellen SB, 1997)
- The EuroQoL 5-Dimensions 5-Level (EQ-5D-5L) (Section 10.11.2) is a self-assessed, standardized instrument to measure health-related quality of life and has been used in a wide range of health conditions. The EQ-5D-5L comprises 5 dimensions, each describing a different aspect of health: mobility, self-care, usual activities, pain/discomfort, and anxiety/depression.
- The Kidney Disease Quality of Life instrument-36 items (KDQOL-36TM) (Section 10.11.3) is a 36-item kidney-specific health-related quality of life measure including Short-Form Health Survey 12 Item (SF-12) as generic core plus the burden of kidney disease, symptoms/problems of kidney disease, and effects of kidney disease scales.

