##### **9.4.5.1. Quality of Life**

The following quality of life assessments will be summarized by treatment group at baseline and each postbaseline time point using descriptive statistics for the observed value as well as the change from baseline:

- EQ-5D-5L
- KDQOL-36

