7.5.2. Patient-Reported Outcomes

Quality of life will be analyzed for EQ-5D-5L and KDQOL-36.

For EQ-5D-5L, a visual analogue scale (VAS) and the health state index score using US time trade-off (TTO) will be calculated (based on Section 9.3.13) and summarized at Baseline and each scheduled post-Baseline time point using descriptive statistics for continuous variables for the observed value as well as the change from Baseline.

For KDQOL-36, Short-Form Health Survey 12 Item (SF-12, item 1-12), burden of kidney disease (item 13-16), symptoms/problems of kidney disease (item 17-28b), and effects of kidney disease scales on daily like (item 29-36) as subscales will be calculated separately by taking the sum of the component items. Descriptive statistics as well as the change from Baseline by visits will be presented separately for each subscale.

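### The SAP carries the EQ-5D-5L index forward without limit when the whole form is missing, although both documents say observed values are summarised

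*SAP*

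**What the plan says.** SAP 9.3.13 scores the index as "US TTO score = 1 + MOBILITY + SELF CARE + USUAL ACTIVITIES + PAIN/DISCOMFORT + ANXIETY/DEPRESSION", using the listed decrements, and then gives two missing-data rules. For a partly completed form, "data for the missing dimension(s) from the last available assessment prior to the time point with missing data will be used". For a form with nothing completed, "If all dimensions are missing, the last available US TTO score prior to the time point with missing data will be used". Neither rule sets a limit on elapsed time or refers to the reason the data are missing.

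SAP 7.5.2 says the index and the VAS are summarised at Baseline and at each scheduled later time point by "descriptive statistics for continuous variables for the observed value as well as the change from Baseline". Protocol 9.4.5.1 says the same of EQ-5D-5L and KDQOL-36: "using descriptive statistics for the observed value as well as the change from baseline". Neither section mentions carrying a score forward.

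Protocol 8.11.1 covers participants judged "not able to self-report using any of these instruments at a particular time point, then they will not be administered to the participant". For them every dimension is missing at that visit.

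FACIT-Fatigue (SAP 9.3.14) and KDQOL-36 (SAP 9.3.15) are prorated within a form and left uncalculated when more than half the items are missing. Neither borrows from an earlier visit.

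SAP Section 4 reports 16 participants enrolled. It also reports a decision to end the study once the last participant on treatment finishes the 26-week Treatment Period.

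**The concern.** A form that was never completed enters the visit summary as if it had been. Three effects follow.

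- **n is overstated.** The table shows data at visits where none were collected.
- **Change is pulled toward zero.** A carried baseline score gives a change of exactly 0, which dilutes improvement or worsening in those who did respond.
- **The gaps are unlikely to be random.** Protocol 8.11.1 withholds the questionnaire from participants who cannot self-report, so a sick participant can be represented by a score from a better day.

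The termination adds a fourth route. A participant who finishes Week 26 as the study closes has no Week 34 or Week 52 form, and the wording would fill both visits with an earlier score.

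What is at stake is whether a reader of the EQ-5D-5L table can tell how many people answered and what they said.

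**Working it through.** The plan states no figure on this point, so there is nothing to reproduce. The check compares the sections and then works an illustration with the SAP's own coefficients.

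**1. Visits exposed.** Protocol Tables 1 and 2 schedule the questionnaires at Day 1 and Weeks 4, 14, 26, 34 and 52. A participant with only a Day 1 form can therefore receive at most five carried values. A participant with no Day 1 form and no later one has nothing to carry.

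**2. Index values (SAP 9.3.13).**
- State 22222: 1 − 0.096 − 0.089 − 0.068 − 0.060 − 0.057 = 0.630
- State 33333: 1 − 0.122 − 0.107 − 0.101 − 0.098 − 0.123 = 0.449
- Change from 33333 to 22222: 0.630 − 0.449 = 0.181

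**3. Illustration.** Assumptions, none of them from the documents: 8 per arm (16 enrolled, 1:1 randomization, actual split not stated); everyone starts at 33333; those who respond later are at 22222; k participants have no form after Day 1.
- Carried mean index = [(8 − k) × 0.630 + k × 0.449] / 8
- Carried mean change = [(8 − k) × 0.181 + k × 0] / 8
- Observed-only: mean index 0.630 and mean change 0.181, on n = 8 − k

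| k | Mean index, carried (n = 8) | Mean change, carried (n = 8) | Mean index, observed | Mean change, observed | Observed n |
|---|---|---|---|---|---|
| 0 | 0.630 | 0.181 | 0.630 | 0.181 | 8 |
| 1 | 0.607 | 0.158 | 0.630 | 0.181 | 7 |
| 2 | 0.585 | 0.136 | 0.630 | 0.181 | 6 |
| 3 | 0.562 | 0.113 | 0.630 | 0.181 | 5 |

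For k = 2: (6 × 0.630 + 2 × 0.449) / 8 = 4.678 / 8 = 0.585, and (6 × 0.181) / 8 = 1.086 / 8 = 0.136.

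**4. What does not depend on the assumed states.** When the carried score is the baseline score, the mean change is the responders' mean change multiplied by (n − k)/n. With n = 8 the factors are 7/8 = 0.875, 6/8 = 0.75 and 5/8 = 0.625. The shrinkage is toward zero whichever way the responders moved. If the last score came from a later visit, that visit's change is repeated instead.

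**5. The sections side by side.** SAP 9.3.13 produces a value at a visit where nothing was recorded. SAP 7.5.2 and Protocol 9.4.5.1 call for the observed value at that visit. Both cannot describe the same table.

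**The case against.** The strongest reply is that the consequence is small. EQ-5D-5L is exploratory, SAP 4.2 removes all treatment comparisons, and 16 participants were enrolled. Deaths are reported elsewhere in the SAP: overall survival (5.3), the number who died (7.7.2.1) and a listing (7.7.2.5). All of that stands and sets the weight of the point. It could also be said that observed value is only table language to set a level apart from a change. Even so, a reader would not expect the level to come from another visit.

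Several stronger readings are tempting, and the documents do not support them.

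- **That deceased participants will definitely contribute a score.** SAP 9.3.13 does not mention death or withdrawal. The wording is unrestricted, so it permits this, but a programmer could reasonably stop at death.
- **That only EQ-5D-5L is imputed.** SAP 9.3.10 sets eGFR to 10 during dialysis, and FACIT-Fatigue and KDQOL-36 are prorated. The distinction is carrying a patient-reported score across visits.
- **That SAP 7.1.1 is contradicted.** Its statement "Summary statistics will be provided using observed data" is written for the continuous secondary endpoint and does not govern an exploratory index.
- **That the bias can be sized by scoring death as 0.** Neither document gives a value for death, and that comparison is not with the proposed remedy.
- **That observed-only summaries remove the bias from deaths.** They drop those participants altogether. In the table above the observed mean change is larger than the carried one, so it can look more favourable.
- **That the partly-missing rule is equally at fault.** Nothing here makes a case against it.

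**Conclusion.** The point holds in a limited form. SAP 9.3.13 carries a whole-form missing index forward with no limit or exception, and this conflicts with the summaries described in SAP 7.5.2 and Protocol 9.4.5.1. As written, it overstates n at later visits and shrinks mean change by (n − k)/n when only a baseline score exists. With two of eight missing, that is 0.136 on n = 8 instead of 0.181 on n = 6.

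These figures rest on the assumed arm size, health states and number missing; the documents give no rate of missing forms. The multiplier depends only on the arm size, the number missing and the carried score being the baseline score. The direction of any bias against the true state of the missing participants cannot be settled from the documents.

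The effect is confined to the index. No carry-forward is stated for the VAS, and no primary or secondary result is touched. It is worth correcting because the correction is cheap and the table would otherwise show data that were not collected.

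**What to change.** In SAP 9.3.13, delete the sentence that carries the index forward when all dimensions are missing, and say that the index is then left missing. In SAP 7.5.2, state that observed index values and changes are summarised with n at each visit. Beside the table, show deaths and the reasons for missing forms by arm (withdrawal, unable to self-report, follow-up ended by the termination), with a note that the means describe surviving participants able to respond. Do not assign an index value for death. The rule for partly completed forms can stay.

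The cost is SAP wording and one small display, with no new data collection. The downside is a smaller n at late visits, which is the number of forms available.
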